For a boy, $-1.259 Ht^5 + 7.815 Ht^4 - 18.57 Ht^3 + 21.39 Ht^2 - 11.71 Ht + 2.628$

For a girl, $-4.536 Ht^5 + 27.16 Ht^4 - 63.47 Ht^3 + 72.43 Ht^2 - 40.06 Ht + 8.778$

Uemura O, et al. Clin Exp Nephrol. 2014 [14]

Follow-up laboratory tests should be performed to determine whether the subject continue the study or not, in case of acute deterioration of renal function (eg, $\geq 50\%$ reduction in eGFR or less than 30 mL/min/1.73 m² or serum potassium value over 5.5 mEq/L) (See Section 7.5).

If subjects experience ALT or AST $> 3 \times$ ULN after the start of the Run-in Period (Week -2), follow-up laboratory tests (at a minimum, ALP [serum], ALT, AST, bilirubin [total bilirubin], GGT, and INR) should be performed within a maximum of 7 days and preferably within 48-72 hours after the abnormality was noted (Please refer to Section 7.5 for discontinuation criteria, and Section 10.2.3 for the appropriate guidance on Reporting of Abnormal Liver Function Tests in relation to ALT or AST $> 3 \times$ ULN in conjunction with total bilirubin $> 2 \times$ ULN.).

If the ALT or AST remains elevated $> 3 \times$ ULN on these 2 consecutive occasions the investigator must contact the Medical Monitor for consideration of additional testing, close monitoring, possible discontinuation of study drug, discussion of the relevant subject details and possible alternative etiologies. The abnormality should be recorded as an AE (please refer to Section 10.2.3 Reporting of Abnormal Liver Function Tests for reporting requirements).

Only female subjects of childbearing potential, defined by the investigator's or subinvestigator's positive opinion about the subject's reproductive potential, will undergo a qualitative hCG pregnancy test. The local laboratory will perform the test.

The investigator or subinvestigator is reviewing and filing the laboratory results. The investigator will maintain a copy of the normal reference ranges including the archival records for the laboratory used.

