- Achievement of target blood pressure on each measuring day: Subjects are determined to have achieved their target blood pressures if their blood pressures are the < 95th percentile (both diastolic and systolic) shown in Table 5.a Reference Blood Pressure Values of Children by Gender and Age for essential hypertension or < 90th percentile (both diastolic and systolic) shown in Table 5.a Reference Blood Pressure Values of Children by Gender and Age for secondary hypertension. If either systolic or diastolic blood pressure is missing, it will be handled as missing data. The age at the time of informed consent will be used.

- Disease duration (years): (Date of informed consent [year and month] Time of onset [or diagnosis] of underlying disease [year and month]) / 12 (rounded to 1 decimal place) For the date of informed consent, only the year and month will be used. If the year of onset (or diagnosis) of underlying disease is unknown, it will be classified as "Unknown." If only the month of onset (or diagnosis) of underlying disease is unknown, the disease duration will be calculated with the month of onset (or diagnosis) of underlying disease as January.
- QTcF interval: Fridericia's formula (QT interval / [RR interval^{0.33}])
- CV (%): Standard deviation / mean × 100

7.1.2 **Definition of Study Days**

- Study Day: The day before the first study drug administration for the Treatment Period will be defined as Day -1 and the day of the first study drug administration for the Treatment Period will be defined as Day 1.
- Follow-up Day: The day after the last study drug administration for the Treatment Period will be defined as Follow-up Day 1.

7.1.3 **Definition of Study Visit Windows**

For each test, observation, and endpoint except for home blood pressure, all evaluable data (i.e., non-missing data) will be handled according to the following rules.

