For each visit other than the End of Treatment Period I and the End of Treatment Period, the evaluable data within the acceptable time window will be used. If more than one evaluable datum lies within the same acceptable time window, the data whose test/observation/evaluation time point is closest to the scheduled time point will be used. If there are two data equidistant to the scheduled time point, the data obtained later will be used. The temporal distance from the scheduled time point will be determined based on the Study Day and the time interval between the latest study drug administration and the blood sample collection.

For the End of Treatment Period I and the End of the Treatment Period, the evaluable data within the acceptable time window with the largest Study Day will be used.

Table 7.a Visit Window of Office Sitting Blood Pressure and Pulse Rate

Visit	Cahadulad Study Day	Acceptable Time Window	
Visit	Scheduled Study Day	Study Day	Follow-up Day
At the End of Run-in Period (Week 0)	Study Day: 1	-28 to 1	
Week 2	Study Day: 15	2 to 22	< 4
Week 4	Study Day: 29	23 to 43	< 4
Week 8	Study Day: 57	44 to 71	< 4
Week 12	Study Day: 85	72 to 99	< 4
Week 16 (postdose)	Study Day: 113	100 to 127	< 4
Week 20	Study Day: 141	128 to 155	< 4
Week 24	Study Day: 169	156 to 183	< 4
Week 32	Study Day: 225	184 to 253	< 4
Week 40	Study Day: 281	254 to 323	< 4
Week 52	Study Day: 365	324 to 372	< 4
Week 54 (Follow-up Period)	Study Day: 379	373 to 386	> 0
At the End of Treatment Period I*1		2 to 99	< 4
At the End of Treatment Period*2		2 ≤	< 4

^{*1} Data obtained after the earliest day of addition or dose change of antihypertensive drugs other than RAS inhibitors during the Treatment Period will not be used for summaries. Not applicable for office sitting pulse rate.
*2 The condition of *1 will not apply to this handling. Not applicable for office sitting pulse rate.

Table 7.b Visit Window of Clinical Laboratory Test Items

Visit	Scheduled Study Day	Acceptable Time Window	
V ISIL	Scheduled Study Day	Study Day	Follow-up Day
At the End of Run-in Period (Week 0)	Study Day: 1	-28 to 1	
Week 2	Study Day: 15	2 to 22	< 15
Week 4	Study Day: 29	23 to 43	< 15
Week 8	Study Day: 57	44 to 71	< 15
Week 12	Study Day: 85	72 to 99	< 15
Week 16 (postdose)	Study Day: 113	100 to 141	< 15
Week 24	Study Day: 169	142 to 225	< 15
Week 40	Study Day: 281	226 to 323	< 15
Week 52	Study Day: 365	324 to 379	< 15

Table 7.c Visit Window of Office Standing Blood Pressure and Pulse Rate

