7.11.2 Clinical Laboratory Evaluations

7.11.2.1 Hematology and Serum Chemistry

Analysis Set:

Safety analysis set

Analysis variable(s):

Hematology

Red blood cell count, White blood cell count with differential (neutrophils, basophils, eosinophils, lymphocytes, monocytes), Hemoglobin, Hematocrit, Platelets

Serum Chemistry

ALT, Albumin, ALP, AST, Total bilirubin, BUN, Calcium, Chloride, Creatinine, Creatinine kinase, Cystatin C, eGFR, GGT, Glucose, Total cholesterol, Triglycerides, Phosphate, Potassium, Sodium, Total Protein, LDH

Categories:

Results of determination based on normal reference range [Below lower limit of normal range, Within normal range, Over upper limit of normal range]

Visit:

Weeks 0, 2, 4, 8, 12, 16 (postdose), 24, 40, and 52

Analytical method(s):

The following analysis will be performed for the above analysis variables by weight group ($< 50 \text{ kg}, \ge 50 \text{ kg}$) and in the combined weight groups.

When performing analyses on MAV, if a laboratory parameter has both lower and upper MAV criteria, an analysis will be performed for each. See "9.0 APPENDIX" for test items to be analyzed and definitions of MAV criteria.

The measurement at Week 16 will be performed after the study drug administration, while the measurement at other visits than Week 16 will be performed before the study drug administration.

- (1) Summary statistics for observed values and changes (each visit after administration [Week 2 to Week 52] Week 0) will be provided for each visit.
- (2) Case Plots
- (3) Shift tables showing results of determination based on normal reference range at Week 0 and each visit after administration
- (4) Overall frequency distributions of MAV during the Treatment Period

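### SAP 7.1.3 gives scheduled laboratory samples no priority, so a retest prompted by an abnormal value can replace that value in the by-visit tables when the sample was drawn early or redrawn the same day

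*SAP*

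**What the plan says.** SAP 7.1.3 states that, home blood pressure apart, "all evaluable data (i.e., non-missing data) will be handled according to the following rules". When a window holds more than one value, "the data whose test/observation/evaluation time point is closest to the scheduled time point will be used", and "If there are two data equidistant to the scheduled time point, the data obtained later will be used". Distance is judged on Study Day and on time since the last dose. The rule does not separate scheduled from unscheduled samples.

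SAP 7.11.2.1 then plans by-visit summary statistics, case plots, and "Shift tables showing results of determination based on normal reference range at Week 0 and each visit after administration". It also plans one MAV table for the whole Treatment Period. Under SAP Appendix 9.2 a single qualifying value among all evaluable post-dose data puts the child in that table.

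Protocol 9.1.9 ties repeat testing to abnormal results. For the kidney, "Follow-up laboratory tests should be performed to determine whether the subject continue the study or not, in case of acute deterioration of renal function"; its examples are an eGFR fall of at least 50%, eGFR below 30, and potassium above 5.5 mEq/L. No timing is given. For ALT or AST above 3 × ULN, repeat tests "should be performed within a maximum of 7 days and preferably within 48-72 hours after the abnormality was noted".

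**The concern.** The repeats that the protocol asks for exist only because a first value was abnormal, so the second value in a window is generated by the outcome being measured. A repeat will tend to lie nearer normal, through regression to the mean or because someone acted on the first result. A worsening repeat would also be picked up, but normal values are never replaced by this route.

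Laboratory tests are part of the primary safety endpoint. The protocol expects many children with renal dysfunction and notes that RAS inhibitors may reduce GFR and may be followed by hyperkalaemia. With 50 children planned, one displaced abnormality is 1/50 = 2% of the population. Because the summary statistics include the minimum and maximum, a displaced peak is lost there as well as in the shift table.

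**Working it through.** **Inputs.** Selection and tie rules: SAP 7.1.3. Laboratory windows: SAP Table 7.b (for example Week 4, Day 29, window 23 to 43). Triggers and liver timing: Protocol 9.1.9. MAV limits: SAP Table 9.c. The documents give no figure for how often displacement would occur, so there is none to reproduce.

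**Condition for replacement.** Let the scheduled sample be j days early and the retest r days after it, both in the same window. Their distances from the scheduled day are j and |r − j|. The retest wins, ties included, when |r − j| ≤ j, that is, when r ≤ 2j.

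- r = 2 needs a sample at least 1 day early; r = 3, at least 2 days; r = 7, at least 4 days (whole days).
- A sample on or after the scheduled day, d days late (d ≥ 0), is at distance d. A retest on a later day is at d + r, which is larger, so the first value is kept.
- A same-day redraw ties on Study Day and wins as the later value, unless time since dose separates the two.

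**Example (illustrative values).** Week 4 potassium is 5.8 on Day 27 and 4.6 on repeat on Day 30. The distances are 2 and 1, so Week 4 is reported as 4.6. Since 5.8 does not exceed 6.0, it is not an MAV. If 5.8 is above the laboratory's range and 4.6 within it, the shift table shows normal.

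**Share of recorded retests that displace the first value.** Assumption: visit days are spread evenly over the stated range. The documents do not give the distribution.

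| Retest lag from sampling | Visits within ±3 days | Visits within ±7 days |
|---|---|---|
| 3 days | 2/7 = 29% | 6/15 = 40% |
| 7 days | 0/7 = 0% | 4/15 = 27% |

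The Week 4 window opens only 6 days before Day 29, so at ±7 days its counts fall by one, to 5/15 and 3/15. Averaged over the eight visits, the ±7 figures become (7 × 6 + 5)/120 = 39% and (7 × 4 + 3)/120 = 26%.

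**What the MAV table catches.**

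| Abnormality | Retest trigger in Protocol 9.1.9 | Caught by Table 9.c |
|---|---|---|
| ALT or AST > 3 × ULN | Yes | Yes, same limit |
| eGFR < 30 | Yes | Yes |
| Potassium > 6.0 | Yes | Yes |
| Potassium > 5.5 to 6.0 | Yes | No |
| eGFR fall ≥ 50%, staying ≥ 30 | Yes | No, unless creatinine > 2.0 or BUN > 30 |
| Milder out-of-range values, e.g. ALT between 1 and 3 × ULN | No, but may be repeated | No |

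The last three rows can disappear from both the by-visit tables and the MAV table.

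**The case against.** A reader might infer that on-treatment renal, potassium and liver abnormalities will in general be shown as normal. The documents do not support that.

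- **Liver.** The retest trigger and the MAV limit are the same, so every ALT or AST value that triggers the required repeat is still counted, whichever value the window keeps. eGFR below 30, potassium above 6.0 and creatinine above 2.0 are likewise kept.
- **Timing.** Being a little early is not enough; the sample must be early by at least half the lag. The liver clock also starts when the abnormality is noted, not at sampling. With an assumed laboratory turnaround of 1 to 3 days, the preferred repeat falls about 3 to 6 days after sampling, which gives 40% to 33% (6/15 to 5/15) at ±7 days and 29% to 14% (2/7 to 1/7) at ±3 days.
- **Recording.** Protocol 9.1.9 does not require local renal results during titration to be entered in the eCRF. The renal trigger has no timing, and the two consecutive time points in Protocol 7.5 could be two scheduled visits in different windows.
- **Result.** The shift table reads normal only if the repeat is within range. A child below range at Week 0 reads low to low with either eGFR value; there the loss is in the change summaries.
- **Rule.** Closest-to-schedule is prespecified and makes no reference to the result. A worst-value rule favours abnormality in children sampled more often.

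These points limit the size and scope, but they do not give the scheduled sample priority. The other outputs are partial backstops. The SAP does not say whether case plots show unselected values. Under Protocol 10.1.2 a retest alone does not make a value an adverse event. SAP Table 9.b has no term for raised potassium, raised creatinine or reduced GFR.

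**Conclusion.** The point holds in a limited form. The by-visit laboratory summaries and normal-range shift tables can lose an abnormal scheduled value to a recorded repeat that the value itself prompted. This requires an early sample or a same-day redraw. The MAV table does not make good the loss for potassium above 5.5 up to 6.0, for an eGFR fall of at least 50% that stays at 30 or above (with the creatinine and BUN exception), or for milder out-of-range values.

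The percentages are conditional on a repeat having been made, recorded and placed in the same window, and they rest on evenly spread visit days. The number of children affected cannot be estimated from the documents. Power and alpha are untouched. This is a cheap improvement to a primary safety display; it is not evidence that safety signals will be lost overall.

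**What to change.** In SAP 7.1.3, state that the by-visit laboratory tables use the value from the scheduled visit, and use an unscheduled value only when no scheduled value lies in the window. With that rule no scheduled value is displaced, at any lag or visit offset.

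In SAP 7.11.2.1, add a shift table from Week 0 to the worst on-treatment value over all evaluable data, done separately for the low and high directions, since some analytes can be abnormal both ways. State the cut-off for on-treatment, because Table 7.b accepts samples up to Follow-up Day 14. The MAV analysis needs no change; it already uses all values.

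The cost is a short SAP edit, a sort on visit identifier and one more table. There are two downsides. A kept scheduled value may be a few days further from the nominal day. The worst-value table will also show more abnormalities in children sampled more often, so it should supplement the by-visit table and not replace it.

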8.1.3 Dose and Regimen

During the Run-in Period, subjects will orally receive TAK-536 2.5 mg granules (placebo for the Run-in Period) if subjects weighing < 50 kg, or TAK-536 5 mg tablet (placebo for the Run-in Period) if subjects weighing ≥ 50 kg, once daily, before or after breakfast. During the Treatment Period, the same dose of the selected placebo during the Run-in Period will be the initial dose. After the initial dose, subjects will orally receive any of TAK-536 2.5 mg granules, TAK-536 5 mg, 10 mg, 20 mg tablet, once daily, before or after breakfast, if subjects weighing < 50 kg, or any of TAK-536 5 mg, 10 mg, 20 mg, 40 mg tablet, if subjects weighing ≥ 50 kg. For dose titration method, see Section 6.1 Study Design.

Because weight is likely to change during the study, the highest dose for the subjects is allowed to be changed if dose adjustment by changing of weight is required during the Treatment Period II.

The investigator or subinvestigator may select the timing of the study drug administration (i.e., before or after breakfast) in consideration of subject lifestyle but should not change this timing throughout the study. The investigator or its designee will record the guidance provided about the timing of the study drug administration (before or after breakfast) at the start of the Run-in Period (Week -2) in the eCRF.

At the start of the Run-in Period (Week -2), the study drug for the Run-in Period will be administered on the same day after completing all tests, observations, and evaluations. In case that

subjects take RAS inhibitors in the morning of the visit day, the administration of the study drug for the Run-in Period will be started from the next day.

Except for Week 16, subjects will visit the study site on each visit day without taking the study drugs, and receive them only after completing all tests, observations, and evaluations.

On the visit of Week 16, subjects, the subjects' parent or the subjects' legal guardian will be instructed to visit the study site after taking the study drug and the tests, observations, and evaluations 2 hour (acceptable time window, 1 to 3 hours) after taking the study drug will be performed.

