13.1.3 Efficacy Analysis

(1) Secondary endpoints and analytical methods

[Secondary endpoints]

Office trough sitting systolic and diastolic blood pressure, proportion of subjects who achieve the target blood pressure

[Analytical methods]

The analyses discussed below will be conducted with the FAS.

Summary statistics (number of subjects, mean, standard deviation, maximum, minimum, and quartiles; hereinafter the same) and 2-sided 95% confidence intervals for mean values will be calculated for the office trough sitting systolic and diastolic blood pressure at each time point (including the end of the Treatment Period I and the end of the Treatment Period II; hereinafter the same).

Summary statistics and 2-sided 95% confidence intervals for mean values will be calculated referring to a 1-sample t-test for the change of office trough sitting systolic and diastolic blood pressure from the end of the Run-in Period (Week 0) to each time point during the Treatment Period.

The proportion of subjects who achieve the target blood pressure at each time point during the Treatment Period will be summarized.

(2) Data conversion methods and handling of missing data

Details of data conversion methods and handling of missing data will be defined in the Handling Rule for Analysis and SAP.

(3) Significant level and confidence coefficient

Significant level: 5% (2-sided test)

Confidence coefficient: 95% (2-sided estimates)

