5.0 ANALYSIS ENDPOINTS

Primary Efficacy Endpoint

<Safety>

AEs, anthropometric (weight, height, and body mass index [BMI]) measurements, laboratory tests, resting 12-lead electrocardiogram (ECG), and vital signs (office standing blood pressure, office sitting pulse rate, office standing pulse rate, and home sitting blood pressure)

Secondary Efficacy Endpoints

<Efficacy>

Office trough* sitting diastolic and systolic blood pressures

* Trough: The time point immediately before the next dosing, when the blood drug concentration is assumed to be lowest

Proportion of subjects who achieve the target blood pressure**

** Target blood pressure: < 95th percentile shown in Table 5.a Reference Blood Pressure Values of Children by Gender and Age for essential hypertension, < 90th percentile shown in Table 5.a Reference Blood Pressure Values of Children by Gender and Age for secondary hypertension

Table 5.a Reference Blood Pressure Values of Children by Gender and Age

					•	O
		Boy			Girl	
	90th	95th	99th	90th	95th	99th
6 years old	110/70	114/74	121/82	108/70	111/74	119/81
7 years old	111/72	115/76	122/84	109/71	113/75	120/82
8 years old	112/73	116/78	123/86	111/72	115/76	122/83
9 years old	114/75	118/79	125/87	113/73	117/77	124/84
10 years old	115/75	119/80	127/88	115/74	119/78	126/86
11 years old	117/76	121/80	129/88	117/75	121/79	128/87
12 years old	120/76	123/81	131/89	119/76	123/80	130/88
13 years old	122/77	126/81	133/89	121/77	124/81	132/89
14 years old	125/78	128/82	136/90	122/78	126/82	133/90
15 years old	127/79	131/83	138/91	123/79	127/83	134/91
16 years old	130/80	134/84	141/92	124/80	128/84	135/91

Systolic/diastolic blood pressures (mmHg, JCS2012)

The 90th, 95th, and 99th indicate 90th, 95th, and 99th percentiles, respectively.

<Pharmacokinetics>

Plasma concentrations of TAK-536 and its metabolites (M-I and M-II)

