7.8 Efficacy Analysis

7.8.1 Primary Efficacy Endpoint(s)

The safety endpoints are the primary endpoints in this study.

7.8.2 **Secondary Efficacy Endpoint(s)**

Analysis set:

Full analysis set

Analysis variable(s):

Office trough sitting diastolic blood pressure

Office trough sitting systolic blood pressure

Proportion of subjects who achieved the target blood pressure

Visit:

Weeks 0, 2, 4, 8, 12, 16 (postdose), 20, 24, 32, 40, 52, 54 (Follow-up Period), at the End of Treatment Period I, and at the End of Treatment Period

Analytical method(s):

The following analyses (1) and (2) will be performed for office trough sitting diastolic and systolic blood pressures by weight group ($< 50 \text{ kg}, \ge 50 \text{ kg}$) and in the combined weight groups.

The following analysis (3) will be performed for the proportion of subjects who achieved the target blood pressure by weight group ($< 50 \text{ kg}, \ge 50 \text{ kg}$) and in the combined weight groups.

The measurement at Week 16 (postdose) will be performed after the study drug administration, while the measurement at other visits than Week 16 (postdose) will be performed before the study drug administration.

- (1) Summary statistics and 2-sided 95% confidence intervals of means at each visit will be calculated.
- (2) Summary statistics and 2-sided 95% confidence intervals of means will be calculated for changes (each visit after Week 2 Week 0) at each visit. For the population in the combined weight groups, a one-sample t-test will be applied for reference.
- (3) Frequency distributions will be provided at each visit and the 2-sided 95% confidence interval of the proportion will be calculated.

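### SAP Table 7.a lets the Week 16 post-dose office blood pressure stand as the End of Treatment Period trough value and target status for a child with no later in-window reading

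*SAP*

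**What the plan says.** SAP 7.1.3 opens by stating that, except for home blood pressure, "all evaluable data (i.e., non-missing data) will be handled according to the following rules". For the two end-of-period rows it then says "the evaluable data within the acceptable time window with the largest Study Day will be used".

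Table 7.a gives the End of Treatment Period row a window of Study Day 2 or later with Follow-up Day below 4. Its footnote reads "The condition of *1 will not apply to this handling" and also takes pulse rate out of scope. The first footnote, which this one lifts, concerns readings after another antihypertensive drug is added or its dose changed. Neither footnote mentions time since dosing. The Week 16 (postdose) row covers Study Days 100 to 127.

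Protocol 8.1.3 has children take the drug before coming to the Week 16 visit, with "evaluations 2 hour (acceptable time window, 1 to 3 hours) after taking the study drug will be performed". Protocol 9.1.5 places office blood pressure at the other visits about 21 to 27 hours after the last dose.

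SAP 5.0 defines trough as "The time point immediately before the next dosing, when the blood drug concentration is assumed to be lowest". SAP 7.8.2 analyses office trough blood pressure and target achievement at a list of visits that ends "54 (Follow-up Period), at the End of Treatment Period I, and at the End of Treatment Period". It says that Week 16 is measured after dosing, "while the measurement at other visits than Week 16 (postdose) will be performed before the study drug administration".

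**The concern.** The End of Treatment Period row carries the last available reading, and its only filters are non-missingness and the day window. The Week 16 window lies wholly inside it. A child who stops after Week 16 without a timely early-termination reading, or who misses every later blood pressure, is therefore summarised with a value taken near the start of the dosing interval under a variable named trough. The same value decides whether that child counts as having reached target.

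What is at stake is the correctness of a label and of a few entries in a secondary efficacy table. The primary endpoints are safety endpoints, and the SAP applies the one-sample t-test on blood pressure change for reference only.

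**Working it through.** **1. The plan's own figure.** SAP 6.0 gives n = 50, diastolic change -6.5 (SD 10.5) mmHg, systolic change -9.5 (SD 15.5) mmHg, a two-sided 0.05 level and at least 90% power at the end of Treatment Period I. The non-centrality is (6.5/10.5) x sqrt(50) = 4.38 for diastolic and (9.5/15.5) x sqrt(50) = 4.33 for systolic. Exact one-sample t-test power is 99.0% and 98.9%, so the claim is reproduced. The End of Treatment Period I row closes at Study Day 99. A Week 16 reading taken in its own window (Days 100 to 127) cannot enter it, so this calculation is untouched.

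**2. Applying the row's rule.** Take the non-missing reading with the largest Study Day, subject to Study Day 2 or later and Follow-up Day below 4. All example children have readings on Days 15, 29, 57, 85 and 113 (post-dose).

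| History | Value selected |
|---|---|
| Last dose Day 125, no early-termination reading | Day 113, post-dose |
| Last dose Day 125, reading on Follow-up Day 7 (Day 132) | Day 113, post-dose |
| Last dose Day 125, reading on Follow-up Day 2 (Day 127) | Day 127 |
| Continues past Week 20, reading on Day 141 | Day 141, trough |
| Completer | Day 365, trough |

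The gap is real in the first two rows and absent in the others. In the third row the genuine final reading falls on a Study Day inside the Week 16 window, which matters for the fix.

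**3. How many children.** The documents give no drop-out rate. Assume that 5 to 10 of 50 stop early, evenly over 364 days. The interval from the Week 16 visit (Day 113) to the Week 20 visit (Day 141) holds (141 - 113)/364 = 28/364 = 7.7% of stops.
- No timely early-termination reading in any of them: 5 x 0.0769 = 0.38 to 10 x 0.0769 = 0.77 children.
- A timely reading in half of them (assumed): 0.19 to 0.38.
- Chance of at least one affected child (Poisson): 1 - exp(-0.19) = 17% to 1 - exp(-0.77) = 54%.

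**4. Effect per child.** The documents do not give the difference between the post-dose reading and the reading that would replace it. Assume 3 to 8 mmHg, sign unknown.
- Mean change: 3/50 = 0.06 to 8/50 = 0.16 mmHg.
- Target proportion: at most 1/50 = 2 points.

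**5. Yardstick.** With the planning SDs, which refer to the end of Treatment Period I, the 95% half-width is 2.0096 x 10.5/7.071 = 2.98 mmHg diastolic and 2.0096 x 15.5/7.071 = 4.41 mmHg systolic. For a proportion of 50% it is 1.96 x sqrt(0.25/50) = 13.9 points. At the top of the assumed range, one child moves the mean by 0.16/2.98 = 5% or 0.16/4.41 = 4% of a half-width.

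**The case against.** The best defence is that SAP 7.8.2 already describes every visit other than Week 16 (postdose) as measured before dosing, and End of Treatment Period is one of the listed visits. That shows the intent. It describes when measurements happen and does not choose among readings; the choice is made in 7.1.3. Nor can the word trough act as a filter, because 7.8.2 lists Week 16 (postdose) under the same trough variables.

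A second defence is that the row is meant as a last-on-treatment summary. It accepts readings up to Follow-up Day 3 and keeps data after added antihypertensive drugs, so it favours recency over strict conditions. This has some force, and recency is what the fix gives up. It does not justify reporting a reading taken 1 to 3 hours after dosing as trough.

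Third, Protocol 7.6 and 9.3.5 seek an early-termination visit. But 9.3.5 asks for the blood pressure within 3 days only where possible and allows 14 days for the other tests. A reading taken with those later tests, from Follow-up Day 4, falls outside the row.

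Fourth, Protocol 13.1.1 and 13.1.3 assign data-handling rules to a Handling Rule for Analysis, which was not supplied. It may contain the exclusion. This objection stands: what can be said with confidence is that the SAP text has none.

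Some stronger readings do not hold. A reader might infer that the rule is ambiguous and that two programmers would get different values; it is not, since the largest Study Day gives one answer. A reader might also cite Protocol 13.1.3, where the trough analysis covers time points "including the end of the Treatment Period I and the end of the Treatment Period II; hereinafter the same", as a direct contradiction; that passage lists time points and sets no timing condition. Finally, a reader might extend the point to visits where a child took the morning dose by mistake. That is a separate question, and dose times recorded with plasma samples would not settle it safely: through Week 12 some children also give a post-dose sample after a correctly timed trough reading, so valid troughs could be removed.

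**Conclusion.** The point holds as a minor gap in the SAP. For a child whose last in-window office blood pressure is the Week 16 reading, the stated rule reports a post-dose value as the End of Treatment Period trough and takes target status from it, contrary to SAP 5.0 and 7.8.2.

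Under the assumed drop-out, fewer than one such child is expected. A mean shift of 0.32 mmHg would need two children, each differing by the full 8 mmHg in the same direction; two or more affected children has a probability of about 2% to 18% under the same Poisson model. Drop-out, the share with a timely early-termination reading, and the size and sign of the difference are all assumptions.

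It would be wrong to infer that the efficacy conclusion is at risk. Completers and children with any later in-window reading are unaffected. So are the subgroup analyses, which SAP 7.8.4.7 sets at End of Treatment Period I.

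**What to change.** Add to SAP 7.1.3 and Table 7.a: office blood pressure measured after the same-day dose at the nominal Week 16 visit is not eligible for the End of Treatment Period row, for blood pressure or target status, or for any window other than Week 16 (postdose); the latest remaining eligible reading is used.

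Identify the reading by nominal visit or same-day dosing, not by Study Days 100 to 127. Coding it by day range would discard a genuine early-termination reading such as the Day 127 example. Avoid requiring a pre-dose reading, since no dose follows an early-termination measurement. Confirm that the Handling Rule for Analysis agrees.

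The cost is one sentence and one line of code. The drawback is that the affected child's value is older, normally Week 12 (Day 85 instead of Day 113, 28 days earlier), and may precede a treatment change in Treatment Period II.
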